5.1. Description of the Registry

TRACE is an observational, open-label, single-arm, multi-center registry of subjects who have undergone renal lesion cryoablation per their physician's standard of care. Patients 18 years of age or older who have been determined to be an appropriate candidate for cryoablation will be offered enrollment into the registry. Subjects will be recruited from a variety of practice settings, including academic centers and community-based physicians. Those agreeing to participate in the registry will read and sign an informed consent form prior to their cryoablation procedure. Subjects will be observed for five years from the date of their cryoablation procedure.

The registry is non-interventional; it will neither direct the cryoablation procedures performed nor define the post-surgery follow-up of each subject. A subject's participation in the registry will not influence or direct subject treatment procedures or follow-up care. Physicians will use their discretion and personal standards of care to select subjects, perform the cryoablation procedures and define appropriate follow-up visit schedules for their subjects; it is anticipated that subjects will be seen at least once per year during the five-year follow-up period of TRACE. Subjects may be followed by the physician performing the cryoablation procedure or by their local/personal physician. The enrolling physician will be responsible for providing the follow-up data to the registry and will, as appropriate, work with a subject's local/personal physician to collect the follow-up data.

A subject's Pre-surgery/Enrollment visit will include the collection of general demographics information, a brief medical history (general and renal specific), comorbidities, diagnosis details (imaging, biopsy) and current classes of medications. Subjects will be asked to complete a pre-surgery quality of life (SF-12) questionnaire. At the cryoablation visit, details of the cryotherapy procedure will be collected, as well as any potentially or directly related adverse events.

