3 STUDY OBJECTIVES

The primary objective of the study is to assess the short- and long-term outcomes of patients who undergo renal lesion ablation via cryotherapy with products offered by Galil Medical.

Secondary objectives are:

- Assessment of outcomes across laparoscopic-assisted, percutaneous and open cryoablation procedures.
- Characterization of standards of care for follow-up after cryoablation procedure across the participating registry centers.

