7.2 Adjustments for Covariates

The following covariates will be included, one at a time, in ‘univariable’ Cox regression analysis of time-to-event efficacy endpoints.

- Age (continuous as age*10 to assess 10 year risk)
- Gender
- Race
- Maximum lesion size (≤ 4 cm, > 4 cm) at baseline using the greatest trans-axial diameter
- Number of cryosurgery needles used
- Type of needles used
 - Needles with the cautery feature (IceRod CX, IceFORCE 2.1 CX, IcePearl 2.1 CX) vs other types; a patient is deemed to be in the ‘Needles with the cautery feature’ group if any needle used in that patient was of that type
- Duration (in months) from date of initial diagnosis of the suspicious renal mass to cryoprocedure (continuous variable)
- Baseline eGFR (continuous variable)
- Histological type (conventional renal cell carcinoma [RCC] versus other)
- BMI (continuous variable)
- ASA classification
- NS complexity category at baseline (low, moderate, high) (as defined in Section 6.3)
- Cryoprocedure surgical approach
 - Note: there is only one patient with an open procedure, so only laparoscopic and percutaneous procedures will be included in this analysis
- Prior renal surgery
- Prior abdominal surgery
- Solitary kidney (yes versus no); a patient is considered to have a ‘yes’ for this variable if ‘Nephrectomy’ is selected on the Medical History eCRF page.
- History of hypertension
- History of diabetes
- Use of anticoagulants

All factors in the univariable models with a two-sided p-value < 0.15 will be included in a multivariable analysis to determine the impact of these factors.

The following covariates will be included, one at a time, in ‘univariable’ logistic regression analysis of the occurrence of an adverse event (AE).

- Age (continuous as age*10 to assess 10 year risk)
- Gender
- Race
- Maximum lesion size (≤ 4 cm, > 4 cm) at baseline using the greatest trans-axial diameter
- Number of cryosurgery needles used
- Type of needles used
 - Needles with the cautery feature (IceRod CX, IceFORCE 2.1 CX, IcePearl 2.1 CX) vs other types; a patient is deemed to be in the ‘Needles with the cautery feature’ group if any needle used in that patient was of that type
- Histological type (conventional renal cell carcinoma [RCC] versus other)
- BMI (continuous variable)
- ASA classification
- NS complexity category at baseline (low, moderate, high) (as defined in Section 6.3)
- Cryoprocedure surgical approach

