 - Note: there is only one patient with an open procedure, so only laparoscopic and percutaneous procedures will be included in this analysis
- Prior renal surgery
- Prior abdominal surgery
- Solitary kidney (yes versus no); a patient is considered to have a ‘yes’ for this variable if ‘Nephrectomy’ is selected on the Medical History eCRF page.
- Baseline lesion classification (i.e., exophytic, mesophytic, endophytic).
- History of hypertension
- History of diabetes
- Use of anticoagulants

All factors in the univariable model with a two-sided p-value < 0.15 will be included in a multivariable analysis to determine the impact of these factors.

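### The only adjusted comparison of surgical approaches depends on a univariable p < 0.15 screen, so it can be missing or can omit key confounders by chance

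*SAP*

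**What the plan says.** - **Objective.** SAP 3 lists as a secondary objective: "Assessment of outcomes across laparoscopic-assisted, percutaneous and open cryoablation procedures". Protocol section 4 has the same objective.
- **Allocation.** Protocol 5.1 describes a non-interventional registry: "Physicians will use their discretion and personal standards of care to select subjects". The same sentence extends that discretion to how the procedure is performed.
- **Time-to-event models.** SAP 7.2: "The following covariates will be included, one at a time, in ‘univariable’ Cox regression analysis of time-to-event efficacy endpoints". The list has 19 covariates. It includes approach (laparoscopic and percutaneous only, because one patient had an open procedure), age, ASA class, "Maximum lesion size (≤ 4 cm, > 4 cm) at baseline using the greatest trans-axial diameter" and "NS complexity category at baseline (low, moderate, high) (as defined in Section 6.3").
- **Screen.** SAP 7.2 then states: "All factors in the univariable models with a two-sided p-value < 0.15 will be included in a multivariable analysis to determine the impact of these" (covariates). No term is exempt.
- **AE model.** The logistic model for AE occurrence has 18 candidates, approach among them, and the same rule: "All factors in the univariable model with a two-sided p-value < 0.15 will be included in a multivariable analysis".
- **Other results by approach.** Recurrence and progression with enhancement (SAP 8.6.4), SF-12 (8.6.7), lesion status (8.6.9.1) and AE counts (8.7.2) are shown by approach without adjustment for lesion or patient characteristics. SAP 8.7.1 tabulates approach by NS category. SAP 8.6.6 specifies no Kaplan-Meier curves by approach.

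**The concern.** A univariable p-value measures a factor's crude association with outcome. It does not show whether that factor distorts the comparison of approaches. If lesion complexity, age or comorbidity differs between laparoscopic and percutaneous patients, two things can go wrong. Confounding can mask a real approach difference in the crude screen, so that approach never reaches the multivariable model. Or approach can enter while a real confounder misses the cut-off by chance, so that the estimate is labelled multivariable but is not adjusted for what matters. In either case the secondary objective would rest on crude or partly adjusted figures.

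**Working it through.** **1. Is there another adjusted comparison?** No. Setting SAP 7.2 beside 8.6.4, 8.6.6, 8.6.7, 8.6.9.1, 8.7.1 and 8.7.2 shows no stratified, propensity-based or fixed-covariate comparison of approaches. The table of approach by NS category shows imbalance but does not correct it.

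**2. What must happen for an adjusted estimate to appear?** Approach must have p < 0.15 alone, and so must each confounder. Approach passing alone does not secure adjustment.

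**3. How often would approach fail its own screen?** There is no figure in the plan to reproduce: SAP 4.4 says no power calculation was done. Events, split and hazard ratio (HR) below are assumptions.

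- SE(log HR) = 1/√(events × p × (1 − p)), where p is the share in one approach group.
- Two-sided 0.15 gives a cut-off of 1.44. With m = log(HR)/SE, P(fail) = Φ(1.44 − m) − Φ(−1.44 − m).
- HR 2.0, 20 events, 50:50: SE = 1/√(20 × 0.25) = 0.447; m = 0.693/0.447 = 1.55; P(fail) = 0.456 − 0.001 = 0.455.
- 30:70: SE = 1/√(20 × 0.21) = 0.488; m = 1.42; P(fail) = 0.508 − 0.002 = 0.506.
- 15:85: SE = 1/√(20 × 0.1275) = 0.626; m = 1.11; P(fail) = 0.630 − 0.005 = 0.625.

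Probability that approach fails the screen, true HR 2.0, same formula (unrounded inputs):

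| Events | 50:50 | 30:70 | 15:85 |
|---|---|---|---|
| 10 | 63% | 66% | 73% |
| 20 | 45% | 51% | 62% |
| 30 | 32% | 38% | 53% |
| 40 | 23% | 28% | 45% |

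At HR 1.5 and 20 events with a 50:50 split, the figure is 69%. These figures assume no confounding, so they describe the screen and not the size of any bias.

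**4. What does confounding add?** A Cox simulation used 250 patients, 1,500 replicates per scenario, and censoring uniform over 1 to 7 years, capped at 5. It assumed about 20% of lesions > 4 cm (HR 2.0), NS HR 1.5 per level, and a mean of 13 to 36 events. Two scenarios had no selection. In the other eight, the odds of percutaneous treatment were multiplied by 0.5 for a large lesion and 0.6 per NS level, or by 2.0 and 1.6.

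- Lesion size passed its screen in 44% to 86% of runs and NS in 36% to 80%, although both were true predictors.
- Approach was dropped in 12% to 84% of runs. It entered without both size and NS in 11% to 36%.
- All three entered together in 4% to 64% of runs, and in no more than 12% in eight of the ten scenarios.
- With a true approach HR of 1.5 and percutaneous treatment favoured for smaller, simpler lesions, the median crude HR was 1.17 to 1.19 and approach was dropped in 81% to 82% of runs. With size and NS forced in, the median was 1.52 to 1.54.

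The forced model recovers the truth here largely by construction, because it contains exactly the confounders simulated. It does not show that a small model would remove all confounding in TRACE.

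**The case against.** The plan does not claim a causal comparison. SAP 4.4 calls the study non-comparative and not powered for formal analysis, and the protocol synopsis says only that relative efficacy in subgroups may be explored. The screened model can fairly be read as an exploration of prognostic factors, for which a liberal screen is common. That stands, and it limits the weight of the point: this concerns the interpretation of a secondary objective, not a primary test. It does not remove the gap, because the SAP still plans a multivariable analysis and low power makes p-value screening less dependable.

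A reader might infer that the approach comparison is bound to be confounded or dropped. The documents do not support that. The univariable Cox model for approach is always fitted, and the example code in SAP Appendix 2 requests confidence limits. The one-way summaries appear regardless, and an adjusted estimate exists whenever approach and the confounders all pass. Nor do the documents say that approach was chosen by lesion size or comorbidity; that is plausible under physician discretion, but not shown.

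A reader might also take the failure rates as predictions for TRACE. They are not: every event count, split and HR behind them is assumed.

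**Conclusion.** The point holds in a limited form. The plan guarantees a crude comparison of laparoscopic and percutaneous procedures but not an adjusted one, and it does not fix which confounders any adjusted estimate would contain. That follows from the text of SAP 7.2 and needs no assumption. Its practical size does: at a true HR of 2.0 and 20 events, approach would fail its own screen in roughly 45% to 62% of cases over splits from 50:50 to 15:85, before any confounding. This is a cheap improvement worth making, not a defect that invalidates the registry's results.

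**What to change.** For each time-to-event endpoint and for AE occurrence, add one fixed laparoscopic-versus-percutaneous model with a small confounder set entered whatever the p-values:

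- **Recurrence and AEs:** NS complexity or lesion size. Not both are needed, because the radius component of NS already scores size (SAP 6.3).
- **Overall survival:** the same, plus age and ASA class, since comorbidity bears on death from any cause.
- **Disease-specific survival:** name the set in advance; the lesion covariate is the natural minimum.

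Use a Firth penalty if events are few. Approach plus three-level NS takes 1 + 2 = 3 parameters, or 20/3 ≈ 7 events each at an assumed 20 events; approach plus binary size takes 2, or 10 each. Report the approach estimate with its 95% CI, state that open procedures (one patient) cannot be assessed, and keep the screened models as exploratory.

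SAP 5.2 records a Steering Committee review of draft tables dated 8 May 2018, so the SAP should label these models as added after that review.

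The cost is one extra model per endpoint on variables already in the SAP 7.2 lists. Intervals will be wide with few events, and residual confounding may remain.

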7.3 Handling of Dropouts or Missing Data

Dropout patients will not be replaced in this study. The handling of missing data will be discussed throughout Section 8, where relevant. Censoring for the efficacy endpoints is discussed in Sections 6.4.1 and throughout Section 8, where applicable.

7.4 Interim Analyses

Interim analyses will be performed as requested by the Steering Committee.

7.5 Multiple Comparisons/Multiplicity

Since this is a single arm registry study, no adjustment for multiple testing will be performed.

7.6 Examination of Subgroups

Subgroup analyses required for individual endpoints are described in Section 8.

8 STATISTICAL ANALYSIS

8.1 Disposition of Patients

The number of patients enrolled will be summarized by analysis population (see Section 8.3) and by site. The number of patients who completed the study, the number of patients ongoing in the study (for interim analyses), and the number of patients who discontinued from the study and the reasons for discontinuing (e.g., withdrew consent, lost to follow-up, death, other) will also be summarized.

Duration of follow-up is defined as the time from cryoprocedure until date of death due to any cause or date when patient was known to be alive.

Duration of follow-up (months) =

$$(\text{Date of death/last known alive} - \text{Date of cryoprocedure} + 1) / 30.4375$$

Duration of follow-up will be summarized using descriptive statistics. The number and percentage of patients with follow-up up to the following timepoints will also be provided:

- 1 month
- 3 months
- 6 months
- 12 months
- 24 months
- 36 months
- 48 months
- 60 months.

The number of patients who have completed each follow-up visit will be provided based on the analysis windows derived from the lesion assessment follow-up dates. The corresponding percentage of patients will be based on the number of patients who remain in follow-up at that visit (i.e. excluding patients who have withdrawn, died or completed after the end date of the analysis window). For example, if a patient withdrew from the study or died within the 36 month analysis visit window, the patient would be included in

the 36 month visit percentage calculation, but would not be included in the percentage calculations for subsequent visits.

The number of patients censored for the time-to-event endpoints, together with a breakdown of the reasons for censoring, will also be summarized.

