Key Exclusion Criteria	
 1. Patient is either currently using or has used within the last 30 days an investigational product of any type. 2. Patient has metastatic disease to or from the kidney. 3. Patient has had previous therapy on the index lesion (e.g. radiofrequency, cryoablation, partial nephrectomy).
Renal Lesion Size Criteria	While there are no strict exclusion criteria with regard to lesion size, the typical renal lesion suitable for cryoablation is ≤ 4 cm. Physicians are to use their training and experience to determine the size of a renal lesion that is appropriate for cryoablation.
Statistical Methods	
Continuous variables (e.g., age) will be summarized by the number of subjects, mean, standard deviation, median, minimum and maximum. Categorical variables (e.g., race) will be summarized by frequencies and percentages of subjects in each category.
 
Reporting from the database will include:
 
 • Baseline demographics and disease status will be summarized. • Disease recurrence or progression will be summarized. • Survival and disease-specific survival rates will be summarized at given time points. • Overall survival (time to death) disease-specific survival (time to death of kidney cancer), and recurrence free survival (time to disease recurrence or progression) will be analyzed using the Kaplan-Meier methodology and presented graphically. • Follow-up patterns across physicians/centers will be summarized. • Lesion size reduction will be analyzed. • Relative efficacy in subject subgroups may be explored.

Table of Contents

Protocol Synopsis	iii
Table of Contents	vi
1. Background	1
1.1. Cryotherapy	1
1.2. Cryo-Technology	1
2. Device Description	1
2.1. Cryotherapy Systems	1
3. Registry Rationale	2
4. Registry Objectives	2
5. Registry Design	3
5.1. Description of the Registry	3
6. Registry Population	4
6.1. Subject Enrollment	4
6.2. Inclusion Criteria	4
6.3. Exclusion Criteria	4
6.4. Renal Lesion Size	5
6.5. Withdrawal of Subjects	5
7. Registry Assessments	6
7.1. Pre-Cryoablation Evaluation	7
7.2. Cryoablation Procedure	8
7.3. Early Complications	9
7.4. First Post-Operative Follow-Up	9
7.5. Ongoing Follow-Up Visits	9
7.6. Withdrawal	9
8. Statistical Methods	10
8.1. Sample Size Estimate and Justification	10
8.2. Missing Data	10
8.3. Analysis Populations	10
8.4. Measures	10
8.5. Analyses	12
9. Data Management	13
9.1. Data Collection	13
9.2. Data Processing	13

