The primary objective of the registry is to assess the short- and long-term outcomes of subjects who undergo renal lesion ablation via cryotherapy with products offered by Galil Medical.

Secondary objectives are:

- An assessment of outcomes across laparoscopic-assisted, percutaneous and open cryoablation procedures.
- Characterization of standards of care for cryoablation procedure follow-up across the participating registry centers.

5. Registry Design

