4 STUDY DESIGN

4.1 General Design

This is an observational, open-label, single-arm, multi-center study of patients who have undergone renal lesion cryoablation per their physician's standard of care via a Galil Medical cryoablation system using Galil Medical needles.

Data for patients who agree to participate are collected prospectively. (i.e., registry data collection).

TRACE is anticipated to enroll approximately 250 patients at approximately 10 sites.

Patients will be enrolled from a mix of academic and community-based sites.

The schedule and number of follow-up visits for each patient will be determined by his/her physician's standard of care.

Within this context, semi-annual to annual follow-up during the five-year follow-up period is anticipated though it is recognized that follow-up schedules will vary among enrolled patients. Planned per-patient follow-up is 5 years.

The results generated by the registry database will evaluate the use, safety and effectiveness of cryotherapy for renal lesions and will assess the potential advantages and disadvantages of the procedure (e.g., disease recurrence or progression, disease-specific survival rates, overall survival rates, etc).

It will also provide information on long-term surveillance of patients undergoing renal lesion cryoablation.

In addition, this registry may be used as a continuous quality improvement tool on behalf of the treating physicians and will contribute to the development and refinement of standards of care for treatment and follow-up assessments.

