8.8 Other Analyses

8.8.1 Post-treatment lesion characteristics

The analyses described in this section will be performed on the ITT and RCC populations.

The following lesion characteristics will be summarized in a per-patient summary, separately for each post treatment visit:

- Duration (months) between date of cryoprocedure and date of imaging will be summarized with descriptive statistics
- The type of imaging used (CT, MRI, ultrasound)
- Number of new lesions identified which were not present at baseline
 - Number of new lesions that are ipsilateral
 - Number of new lesions that are contralateral

The following lesion characteristics will be summarized in a per-lesion summary, separately for each post treatment visit (i.e., over the total number of lesions recorded in the study for descriptive statistics, and as a percentage of the total number of lesions for categorical data):

- Lesion in right or left kidney (right, left)
- Lesion size, by greatest trans-axial diameter, will be summarized with descriptive statistics and also as categories of ≤ 4 cm and > 4 cm
- Lesion volume will be summarized with descriptive statistics
- The type of imaging used (CT, MRI, ultrasound)
- Lesion location
- Lesion classification
- Lesion shape
- Cystic or solid lesion
- Hounsfield units, separately for each of following phases
 - Non-contrast
 - Arterial Phase
 - Venous Phase
 - Delayed Phase
- Area suspicious for lesion recurrence according to Hounsfield units (as defined in Section 6.4.1)
- Biopsy performed?
- Duration (months) between date of cryoprocedure and date of biopsy sample will be summarized with descriptive statistics
- Type of biopsy
- If a core biopsy was performed, number of cores taken
- Frozen section pathology result
- Frozen section pathology classification
- Permanent section pathology result
- Permanent section pathology classification
- Fuhrman classification grade

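### The SAP keeps follow-up standards of care across centers as a secondary objective but specifies no follow-up summary by site

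*SAP*

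**What the plan says.** Protocol section 4 lists as a secondary objective "Characterization of standards of care for cryoablation procedure follow-up across the participating registry centers". SAP section 3 keeps it: "Characterization of standards of care for follow-up after cryoablation procedure across the participating registry centers". The Statistical Methods entry of the protocol synopsis names the matching output: "Follow-up patterns across physicians/centers will be summarized".

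The design leaves follow-up to local practice. SAP 4.1 states: "The schedule and number of follow-up visits for each patient will be determined by" the standard of care of the patient's physician, with semi-annual to annual visits anticipated.

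In SAP 8.1 the site split is attached to enrollment: "The number of patients enrolled will be summarized by analysis population (see Section 8.3) and by site". For follow-up itself the section says "Duration of follow-up will be summarized using descriptive statistics" and "The number of patients who have completed each follow-up visit will be provided based on the analysis windows", with no site split on either. SAP 8.6.10 pools data across sites and plans no poolability assessment.

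**The concern.** Because each physician sets the follow-up schedule, variation between centers is what this objective is about. A pooled figure cannot show it. As an illustration with assumed values and equal site sizes, a pooled 70% with 12-month imaging arises if every site is at 70%, and equally if half the sites are at 95% and half at 45%, since (95 + 45)/2 = 70. The objective is to tell these apart, and no table specified in the SAP does so.

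SAP 5.2 itemizes departures from the protocol, including small ones such as the uncollected needle-cautery item, but is silent on this summary. A reader of the final report would find the objective stated, no between-center result, and no explanation.

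**Working it through.** The plan states no figure for this objective, so there is none to reproduce. The check has three steps.

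**1. Which outputs are split by site?**

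| SAP section | Output | Split by site? | Describes follow-up practice? |
|---|---|---|---|
| 8.1 | Enrollment | Yes | No |
| 8.4 | Baseline biopsy data | Yes | No |
| 8.7.1 | Procedure method, operator, anesthesia | Yes | No |
| 8.7.2 | AE, SAE and UADE totals | Yes | No |
| 8.1 | Duration of follow-up, follow-up to fixed timepoints, window completion | Not stated | Yes |
| 8.6.5 | Follow-up biopsy | Not stated | Yes |
| 8.8.1 | Imaging timing and type, biopsy, per post-treatment visit | Not stated | Yes |
| 8.8.2 | New therapies and retreatment, per visit | Not stated | Yes |

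The SAP asks for a site split where it wants one, and every such request falls outside follow-up practice. SAP 7.6 refers subgroup analyses to section 8, which has none for this.

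**2. Would the 8.1 window table, run by site, be enough?** The windows come from SAP 6.2.2. On-schedule visits are placed at relative day = round(months × 30.4375) + 1.

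- Annual visits at months 12, 24, 36, 48 and 60 fall on days 366, 731, 1097, 1462 and 1827. They fill the 12-, 24-, 36-, 48- and 60-month windows, one visit each.
- A semi-annual schedule adds months 6, 18, 30, 42 and 54, on days 184, 549, 914, 1279 and 1645. Day 184 fills the 6-month window (93 to 275). The other four fall in windows already occupied: 549 in 276–549, 914 in 550–915, 1279 in 916–1281 and 1645 in 1282–1647.
- Ten semi-annual visits therefore fill 6 windows and five annual visits fill 5. The only difference is the 6-month window.

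The added visits sit at or within two days of the upper window edge, so a slightly late one moves to the next window. That window already holds its own annual visit, so the set of filled windows does not change. Completion counts after month 6 thus cannot separate the two schedules that SAP 4.1 anticipates when visits are attended. The interval between assessments can, provided it uses all dates before 6.2.2 reduces each window to one assessment.

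**3. How precise would a by-site percentage be?** SAP 4.1 gives about 250 patients at about 10 sites. Actual site sizes are not given; assuming equal sizes, n = 250/10 = 25. The Wilson interval, with z = 1.96, is

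[p + z²/2n ± z√(p(1−p)/n + z²/4n²)] / (1 + z²/n)

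- p = 0.80: (0.8 + 0.0768)/1.1537 = 0.760; half-width 1.96 × √(0.0064 + 0.0015)/1.1537 = 0.151; interval about 61% to 91%.
- p = 0.50: centre 0.500; half-width 0.182; interval about 32% to 68%.

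**The case against.** The case against has several parts.

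- **The objective is partly served.** The pooled outputs in 8.1, 8.6.5, 8.8.1 and 8.8.2 do describe follow-up over the participating centers, and SAP 7.1 plans listings of all eCRF data. This stands. A reader might infer that the objective cannot be answered at all, or will have no result. The documents do not support that: dates, imaging type and biopsy are collected, and site is already a table split. What is missing is the between-center summary, and a listing is not a summary.
- **The table shells are a separate document** (SAP section 12) and might contain site columns. That cannot be excluded, so the point is limited to the SAP text, which gives the shells no such table to implement.
- **The wording allows other readings.** The objective could mean over all centers taken together, and the by-site layout in 8.1 might carry over to completion and discontinuation counts. The first reading is hard to square with the synopsis, which speaks of patterns across physicians and centers. The second would give disposition by site, not visit schedule or modality.
- **The promise is a single synopsis bullet.** Protocol 8.5 does not repeat it, and protocol 8.3 defers full detail to the SAP. This is true, but the SAP keeps the objective and does not record the analysis as dropped.
- **Recurrence.** A reader might infer that by-site follow-up is needed to judge whether low recurrence merely reflects sparse imaging. The documents do not support resting the point on that. They report no recurrence result, 8.1 already gives pooled lesion-assessment completion per window, and recurrence is not planned by site, so the two could not be matched.

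**Conclusion.** The concern holds as a gap between a retained objective and the specified outputs. Followed as written, the SAP produces no between-center description of follow-up, and 5.2 does not say so. No planned estimate becomes wrong as a result; the loss is the between-center part of one of two secondary objectives.

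It should not be read as saying that everything is pooled, since adverse event totals are given by site, nor that the data fall short.

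The conclusion rests on the SAP text without the shells. The precision figures assume equal sites of about 25; unequal sites and shrinking denominators in later windows would make some intervals wider. That is adequate for description, and the SAP already reports other items by site at these sizes. The finding about windows assumes that visits are attended close to schedule.

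**What to change.** Add to the SAP a descriptive by-site summary, and by physician where that is recorded, of:

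- duration of follow-up;
- number of lesion assessments per patient and median interval between consecutive assessments, from all assessment dates before the one-per-window selection in 6.2.2;
- window completion, as defined in 8.1;
- imaging modality per window;
- follow-up biopsy.

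Show n per site beside every percentage, note the imprecision, and make no between-site tests. If the sponsor decides against this, record in 5.2 that the between-center part of the objective will not be analyzed, with the reason.

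The cost is a by-site run of tables already planned plus one new derived variable, the interval between assessments; 8.8.1 plans only the time from cryoprocedure to imaging. The count per patient comes from the same dates. No new data are needed.
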